**Aim 2.** Using a micro-randomized screening experiment, we will identify efficacious behavioral strategies to produce an acute (within 5 min of receiving the prompt) reduction in SB based on three factors: (a) behavioral target (sit-to-stand vs. sit-to-light physical activities (LPA)); (b) social effects (group vs. individual); and (c) content (Target set vs. No target set). Our primary outcome will be a change from a sitting behavior to a standing behavior within 5 minutes of receiving the prompts. Furthermore, we will look at overall stand time (minutes), steps.

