## 5 Number of Participants

Indicate the total number of participants to be recruited and enrolled: 20

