**Part B (weeks 5-9):**

Participants will be randomized to either receive or not to receive prompts every work hour (8 per day) via email, for 4 weeks. A total of 80 prompts will be sent to participants over a 4-week period during their work hours (9AM-5PM) on workdays.

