### *PART B*

For instances where prompts were sent and a response occurred, the response time will be recorded (seconds) and the average response time calculated. The number of responses occurring each hour will be calculated to identify the frequency of responses by hour. Generalized estimating equations (GEEs) will be ran using GENMOD (with a repeated statement) to examine the main effect of prompt delivery (sent or not sent) by modeling the mean likelihood of a response as an odds ratio, over the next 5-minute and 30-minute periods. An autoregressive model will be used to account for time dependency and the correlation between observations. Mixed model analyses will be conducted using PROC MIXED to examine the association between prompt type and total sedentary time over the next 5-minute and 30-minute period. All models will be adjusted for age, race, gender, day of intervention and minutes of sitting 30 minutes prior to a prompt. Decision points where the participant was standing or moving at the time of prompt delivery (sent) or scheduled (not sent) time will be excluded from analyses.

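### The Part B GEE names no standard-error type or small-sample correction for 20 participants; with the usual empirical SE and a normal reference, a nominal 5% test runs at about 7-9%

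*SAP*

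**What the plan says.** The SAP's PART B text gives the whole analysis of the prompt experiment in one paragraph. For prompt delivery it states "Generalized estimating equations (GEEs) will be ran using GENMOD (with a repeated statement", with the purpose "to examine the main effect of prompt delivery (sent or not sent) by modeling the mean likelihood of a response as an odds ratio", over windows of 5 and 30 minutes. On dependence it adds "An autoregressive model will be used to account for time dependency and the correlation between observations". Age, race, gender, day of intervention and recent sitting time are covariates, and decision points at which the participant was not sitting are dropped.

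The protocol, section 5, reads "Indicate the total number of participants to be recruited and enrolled: 20". Section 2, Aim 2, describes the design ("Using a micro-randomized screening experiment, we will identify efficacious behavioral strategies") and the outcome: "Our primary outcome will be a change from a sitting behavior to a standing behavior within 5 minutes of receiving the prompts". Section 7, Part B, says "Participants will be randomized to either receive or not to receive prompts every work hour (8 per day) via email, for 4 weeks" and "A total of 80 prompts will be sent to participants over a 4-week period".

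Neither document states which variable defines the cluster, whether the standard error is empirical or model-based, which reference distribution is used, whether a small-sample correction applies, or the alpha level.

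**The concern.** Each participant contributes up to 160 hourly decision points, so the data set looks large: 20 x 160 = 3,200 points before exclusions. The empirical sandwich variance is nevertheless built from one summed contribution per cluster, and there are 20. With so few clusters it is biased downward, and a normal reference ignores the uncertainty in the variance itself. Both errors make p-values too small and intervals too narrow. More hourly points per person do not help.

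The SAP labels no model as primary, but the 5-minute GEE is the nearest match to the outcome that Aim 2 calls primary. What is at stake is the stated precision of the prompt odds ratio. The problem grows if participants leave during the 10 weeks. Leaving the standard-error type open also means it could be chosen after the results are seen.

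**Working it through.** The plan states no alpha, power or expected response rate, so it has no figure to reproduce.

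**Inputs from the documents.** There are 20 participants (protocol section 5). Decision points per person are 8 per day x 20 workdays = 160 (section 7). Of these, 80 are prompts, and 80/160 is read as 1:1 randomisation within person. The model is a logistic GEE with an autoregressive working correlation and the SAP covariates.

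**Assumed inputs.** Participant as cluster; two-sided 5%; empirical standard error with a normal reference; the response rate; the share of points kept as sitting; the between-person SD of the prompt log-odds ratio (the effect SD).

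**Closed form.** For a mean of n cluster contributions, the uncorrected standard error is low by a factor sqrt((n-1)/n), and the statistic follows t with n-1 degrees of freedom. The true size is

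P(|t(n-1)| > 1.96 x sqrt((n-1)/n)).

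- n = 20: 1.96 x sqrt(19/20) = 1.910, size 7.1% (6.5% from the reference distribution alone)
- n = 16: 1.898, size 7.7%
- n = 12: 1.877, size 8.7%

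This needs no response rate or effect SD.

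**Simulation under the null.** 8,000 trials per setting, Monte Carlo SE about 0.3 points, 60-85% of points kept. Rejection rates with 20 participants:

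| Response rate | Setting | Sandwich, z | Mancl-DeRouen, t(19) |
|---|---|---|---|
| 25% | constant effect | 7.4% | 4.7% |
| 25% | effect SD 0.5 | 7.5% | 4.4% |
| 25% | 60% of points kept | 7.2% | 4.3% |
| 10% | constant effect | 7.6% | 4.6% |
| 10% | effect SD 0.5 | 9.0% | 5.4% |
| 10% | effect SD 0.8, 60% kept | 9.0% | 5.6% |
| 50% | constant effect | 7.5% | 4.5% |
| 50% | effect SD 0.5 | 7.2% | 4.5% |

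Dropping age, race and gender at 25% response leaves the uncorrected rate at 7.5% and 8.0% in two settings, so the person-level covariates are not the cause. With 16 participants the uncorrected rates are 8.0-10.1% (corrected 4.5-5.9%). With 12 the rate is 9.4% (corrected 4.3%).

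**Other simulations with different assumptions.** One set used response rates of 5-30%, person-level intercept SDs of 0.5-1.0 on the logit scale, effect SDs of 0-0.8, and either a common sitting share (50-70%) or one varying by person (20-90%). At 20 participants it gave 6.7-8.5% with a common share and 7.5-9.5% with varying shares. Mancl-DeRouen with t(19) gave 4.0-6.0%. Using t(19) with the uncorrected standard error gave 5.4-7.8%, so changing the reference alone is not enough. A further check gave 6.3-7.6% uncorrected and 3.5-5.1% corrected.

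**Model-based standard error, 20 participants.** Size is 4.9-5.2% with a constant effect and 15-22% with effect SD 0.5-0.8; the further check gave 14-18% when the effect varies.

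**Interval width.** Closed form at n = 20: (2.093/1.96) x sqrt(20/19) = 1.096, or 10% wider. By simulation it is 13-14%. At an illustrative odds ratio of 1.5, the interval 1.27-1.77 becomes 1.25-1.81 with a constant effect, and 1.17-1.93 becomes 1.13-1.99 with effect SD 0.5.

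**The case against.** The documents show only that the standard-error type is unnamed. The 7-9% describes an assumed analysis, and the 9.0% needs a 10% response rate combined with an effect SD of 0.5-0.8. With a constant effect the main simulation gives 7.4-7.6%. This stands, and the figure should be read as conditional. Even so, the closed-form 7.1% needs neither assumption.

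The shift is small, the study calls itself exploratory, and neither illustrative interval changes a conclusion. This is fair and limits the weight of the point. The direction of the error is predictable, though, and Aim 2 seeks efficacious strategies for publication.

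The GEE covers only sent versus not sent. Prompt type, which carries the three factors of Aim 2, goes to PROC MIXED, which was not examined here. That limits the scope but does not answer the point for the GEE.

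All participants come from one employer department and some prompts are group-based, so coworkers' responses may be correlated. The simulations assumed independent participants, so the corrected rates are not guaranteed for this design. The same correlation would affect the uncorrected analysis, so it is no defence of the plan.

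Mancl-DeRouen is slightly conservative in most settings, so part of the widening is over-correction. That is true, and it is the price of holding the level.

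Section 7 could be read as randomising whole participants. Aim 2 and the SAP's sent/not-sent decision points favour the within-person reading. Under the other reading the inflation is larger: about 11% analytically and 13% by simulation.

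**Conclusion.** The concern holds. As written, the GEE leaves open the choices that determine its intervals. With the empirical standard error and a normal reference, a nominal two-sided 5% test has a true size of about 7-9% at 20 participants; individual simulated settings ran from 6.3% to 9.5%. The rate rises with dropout, to 8.0-10.1% at 16 participants in the main simulation. A model-based standard error is no safe default, because it fails badly once the prompt effect differs between people.

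The size rests on the assumed alpha, response rate, sitting share and effect variation, on independence between participants, and on randomisation within person. The inflation is modest and the study exploratory, so this should be corrected but does not undermine the trial.

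**What to change.** Keep the marginal model and add one sentence to the SAP's PART B: the participant is the cluster, and for both the 5-minute and 30-minute GEEs the standard error is a bias-corrected sandwich estimate (Mancl-DeRouen is the one tested here), with tests and intervals from a t distribution on participants analysed minus 1 degrees of freedom (19 if all 20 are analysed).

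This needs a procedure or option that provides the correction, but no new data. The odds ratio itself does not change provided the same estimating equations and working-correlation estimate are kept; if the procedure changes, that should be confirmed. The cost is intervals about 10-14% wider at 20 participants. A sentence acknowledging possible correlation between coworkers would make the remaining assumption explicit.

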**2 Background and Objectives**

Provide the scientific or scholarly background for, rationale for, and significance of the research based on the existing literature and how will it add to existing knowledge.

- Describe the purpose of the study.
- Describe any relevant preliminary data or case studies.
- Describe any past studies that are in conjunction to this study.

The unique attributes of sedentary behavior (SB) (e.g., ubiquitous, habitual, socially-reinforced) and its link to cardiometabolic health risk have led to several studies aimed at understanding the correlates of SB. However, these studies have primarily focused on "static" correlates (e.g., built environment, income status, educational attainment, etc.) and have largely ignored the complex situational, contextual, and dynamic "in the moment" factors that can influence SB.

The development of smart phone apps and wearable devices (e.g. Fitbit, apple watch, jawbone, etc.) within the technology industry has resulted in an increase in personal notifications to stand or move more during the workday. These prompts may vary in medium (phone, email, watch), delivery (textual, visual, sound, vibration) and content (personalized, generic, short, long, motivational, educational, feedback). However, the extent to which these prompts actually reduce SB is not fully understood.

The overall objective of this set of exploratory studies is to understand the personal, behavioral, environmental, and contextual factors that underpin SB and to systematically test a series of contextual prompt characteristics that may lead to subsequent change in SB.

The primary aims are:

**Aim 1.** Using Ecological Momentary Assessment (EMA), we will determine which personal (e.g. fatigue, mood, and stress level), behavioral (e.g. watching TV, working at desk, and eating meals), environmental (e.g. being at home or work, time of the day, and weather) and contextual factors are associated with SB. We will identify the combination of factors most likely to precede and proceed short (<30 min) and long (≥30 min) bouts of SB.

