**SOCIAL BEHAVIORAL INSTRUCTIONS AND TEMPLATE**

NUMBER	DATE	PAGE
HRP-503a	12/21/2017	3 of 6

This 10-week study has 2 main parts: (A) an EMA study and (B) a Screening experiment. Twenty participants will be recruited for the study.

Prior to the start of the study, participants will first have to complete an initial online screening survey to determine eligibility. All eligible participants will be requested to complete an online consent and depending on their smartphone operating system, will be sent instructions (see appendix D, E, F, and G) on how to download the smartphone apps that will be used in the study:

Smartphone App	OS	Description
PACO	Android or iOS	An open-source app designed that will be used to deliver EMA questions randomly throughout a participant's workday.
Daynamica	Android	An app designed to collect user activity and travel data using raw smartphone accelerometer and GOS data.
Prox	iOS	An iOS app designed to capture real-time indoor (office) location through proximity sensors deployed around the workplace.

Eligible and consented participants will be invited to a one-hour orientation session where they will be given detailed information about the study, along with answering any questions or concerns they may have. During this visit, proximity sensors will also be deployed to various key areas in the workplace (i.e., participant's desk, lobby, kitchen, and conference rooms).

Timeline:

	Week									
	Part A				Part B					
Measures	1	2	3	4	5	6	7	8	9	10
Main Survey	X						X			X
Daily logs	X	X	X	X			X	X	X	X
EMA	X	X	X	X						
Prompts							X	X	X	X
ActivPAL	X	X	X	X			X	X	X	X

Throughout Parts A and B (weeks 1-10):

All participants in both part A and B will be asked to complete daily logs that will ask them of the time they went to work and got off of work the previous day, sleep time of the previous night and the time they woke up, and any work-related meetings that they had the previous day. In addition, they will be asked to complete a battery of assessment (see appendix A for list of questionnaires) at three time points in the study: at week 1, 7, and 10. Participants will also be asked to wear the activPAL device on their thigh as an objective measure of sedentary and physical activities. They will be asked to wear the device continuously throughout the study except for the interview weeks (week 5 and 6). The activPAL will be dropped off every Monday morning and picked up every Friday of the same week.

Part A (Weeks 1-4):

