**SOCIAL BEHAVIORAL INSTRUCTIONS AND TEMPLATE**

NUMBER	DATE	PAGE
HRP-503a	12/21/2017	4 of 6

Participants will receive 3 random EMAs (Appendix B) per day throughout the 4-week study. EMAs will only be sent during work hours (9AM-5PM). A total of 1200 EMA observations (3x/day x 20 work days x 20 participants) will be collected.

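### The randomised sent vs not-sent contrast in Part B is valid for the acute 5-minute response, but nothing in the SAP shows whether prompting raises total standing and steps or only moves standing between hours

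*SAP*

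**What the plan says.** Protocol section 2 (Aim 2) looks for strategies "to produce an acute (within 5 min of receiving the prompt) reduction in SB". Its primary outcome is the move from sitting to standing within 5 minutes. It then adds total standing time and steps as further outcomes.

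Protocol section 7, Part B, sets the design: "Participants will be randomized to either receive or not to receive prompts every work hour (8 per day) via email, for 4 weeks". It continues: "A total of 80 prompts will be sent to participants over a 4-week period during their work hours (9AM-5PM) on workdays".

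The SAP (Part B) uses a GEE "to examine the main effect of prompt delivery (sent or not sent) by modeling the mean likelihood of a response as an odds ratio", with 5- and 30-minute windows. A mixed model relates prompt type to sedentary time over the same two windows. The covariates are age, race, gender, intervention day and sitting in the preceding half hour. Decision points at which the person is already up are dropped. There is no term for an earlier prompt, no outcome longer than 30 minutes, and no model for total standing or steps.

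On activPAL wear, Protocol section 7 says: "They will be asked to wear the device continuously throughout the study except for the interview weeks (week 5 and 6". The Timeline accordingly shows the device in weeks 1-4 and 7-10. SAP Part A uses the Part A behaviour data for associations with affect. Part B does not use them.

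**The concern.** The comparator for the prompt effect is a not-sent hour inside the prompted weeks. With hourly decisions, most of these hours come after a prompt on the same day, so they do not represent an unprompted working day. Someone who stood when prompted at 10 may sit through 11, when they would otherwise have got up. Standing has then been moved, not added. The sent vs not-sent difference can look the same in that case as when standing is added.

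The background section of the protocol notes that "the extent to which these prompts actually reduce SB is not fully understood", and Aim 2 goes on to total standing and steps. A large odds ratio could be read as an answer to that wider question, and the planned output would not show whether that reading is right.

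**Working it through.** **Inputs**

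- 8 hourly decisions per workday and 80 prompts over 4 weeks (Protocol section 7, Part B), with the 80 read as per participant.
- 20 workdays and 20 participants: "A total of 1200 EMA observations (3x/day x 20 work days x 20 participants) will be collected" (Protocol section 7, Part A). Here 3 × 20 × 20 = 1,200, so the figure reproduces. The 20 workdays are carried over to Part B.
- The send probability p is not stated.

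**The plan's own figure.** Slots per participant = 8 × 20 = 160, and 80/160 = 0.5. A prompt in every hour would give 160, not 80. The 0.5 is back-solved from the 80, so the match shows consistency and is not independent confirmation.

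**Share of not-sent points that follow a prompt earlier the same day.** With independent hourly randomisation, point k (k = 1 to 8) has at least one earlier prompt with probability 1 − (1 − p)^(k−1). Averaged over k:

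share = 1 − [1 − (1 − p)^8] / (8p)

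At p = 0.5 this is 1 − (1 − 1/256)/4 = 0.751. The share directly after a prompted hour is (7/8) × p = 0.4375.

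| Assumed design | Any earlier prompt that day | Previous hour prompted |
|---|---|---|
| p = 0.3 | 60.7% | 26.3% |
| p = 0.4 | 69.3% | 35.0% |
| p = 0.5 | 75.1% | 43.8% |
| p = 0.6 | 79.2% | 52.5% |
| exactly 4 of 8 each day | 80.0% | 50.0% |

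These shares count all not-sent points, before the seated-only exclusion.

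**Why the planned contrast cannot tell the two cases apart.** The rates below are assumed for illustration and are not from the documents. Take p = 0.5 and let any effect of the previous prompt act equally on sent and not-sent hours, as randomisation implies.

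- *Real gain:* base response 0.20 per hour, prompt +0.15, no effect on the next hour. Sent 0.35, not sent 0.20. Stands per day: 8 × 0.20 = 1.60 unprompted; 8 × (0.35 + 0.20)/2 = 2.20 with prompting. Gain 0.60.
- *Displacement:* base 0.2656, prompt +0.15, next hour −0.15. The average shift is −0.15 × 0.4375 = −0.0656. Sent 0.2656 + 0.15 − 0.0656 = 0.35; not sent 0.2656 − 0.0656 = 0.20. Stands per day: 8 × 0.2656 = 2.125 unprompted; 2.20 with prompting. Gain 0.075.

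In both cases the odds ratio is (0.35/0.65)/(0.20/0.80) = 2.15. The effect of the previous hour's prompt does differ: 0 in the first case, −0.15 in the second. The planned model has no term that would show it.

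**The case against.** The strongest reply is that Aim 2 is about an acute effect in an exploratory screening experiment. Randomising each hour balances prompt history between sent and not-sent points, so the contrast is valid for the 5-minute outcome. That stands in full. A reader might infer that the planned odds ratio is biased for the primary outcome. The documents do not support this, and nothing in the SAP says that the odds ratio will be reported as a net effect. The background sentence on whether prompts reduce sitting concerns commercial notifications and is not a stated aim. The basis for the wider question is Aim 2's mention of total standing and steps.

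Two other strong readings also fail. Part A data do not go unused, because SAP Part A analyses them. And it is the planned model that cannot separate gain from displacement, not the data, because the previous hour's prompt is itself randomised.

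It is also fair that the 75% counts a late-afternoon point after a single morning prompt. At p = 0.5, about 56% of not-sent points (100% − 43.75%) do not directly follow a prompted hour.

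Existing SAP features do not close the gap. The autoregressive structure handles correlation between outcomes, not the effect of an earlier prompt. Intervention day captures trend across days. Sitting in the preceding half hour is not prompt history: if prompts are about an hour apart, the previous prompt and its 5-minute response fall before that window, and an earlier prompt can itself alter the covariate.

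**Conclusion.** The point holds in a limited form. The primary acute comparison is sound. What is missing is any analysis that could support, or argue against, a statement about total standing or steps. About three quarters of not-sent points follow a same-day prompt (61% to 80% over the designs tried), and in the illustration one odds ratio fits gains of 0.60 and 0.08 stands a day.

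This rests on hourly randomisation within person at p of about 0.5. Section 7 could be read as randomising participants, but 80 of 160 slots and the SAP's reference to scheduled but unsent points fit the hourly reading. The documents give no evidence that displacement occurs, only that the plan would not detect it. It is a cheap improvement to the plan, not a flaw in its primary result.

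**What to change.** 1. Keep the randomised sent vs not-sent contrast as primary. State in SAP Part B that it estimates the acute effect, averaged over prompt history, and not the net effect on daily sitting.
2. Add a secondary randomised analysis of sitting, standing and steps over each hour, regressed on the current and the previous-hour prompt. Use all decision points, without the seated-only exclusion and without adjusting for sitting in the preceding half hour, because an earlier prompt can affect both. A lag term added to the existing seated-only model would not be a clean randomised test.
3. Add a supportive within-person comparison of work-hour sitting, standing and step totals in weeks 1-4 against the prompted weeks. Label it non-randomised and open to calendar, EMA (3 a day in Part A) and device-wear effects. Do not make interpretation of the randomised result depend on it.
4. State the send probability. Also reconcile the heading that places Part B in weeks 5-9 with the Timeline, which shows prompts in weeks 7-10, so that the prompted weeks are defined.

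The cost is extra programming on data the protocol already collects. With 20 participants, precision for items 2 and 3 will be limited, so they should be reported as estimates with intervals.

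### Part B plans no estimate of any prompt factor's effect on the Aim 2 primary outcome

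*SAP*

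**What the plan says.** Protocol, section 2, Aim 2, sets the question: "we will identify efficacious behavioral strategies to produce an acute (within 5 min of receiving the prompt) reduction in SB based on three factors". The factors are behavioral target, social effects and content, each at two levels. It then declares the endpoint: "Our primary outcome will be a change from a sitting behavior to a standing behavior within 5 minutes" of a prompt. Two further measures follow: "Furthermore, we will look at overall stand time (minutes), steps".

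Protocol, section 7, Part B, describes the allocation: "Participants will be randomized to either receive or not to receive prompts every work hour (8 per day) via email". It says nothing about how the factor levels are allotted.

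The SAP, Statistical analyses, PART B, has two regression models:

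- A GEE that gives an odds ratio for a response over 5 and 30 minutes. Its stated purpose is to "examine the main effect of prompt delivery (sent or not sent".
- A mixed model to "examine the association between prompt type and total sedentary time over the next 5-minute and 30-minute period".

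Both adjust for age, race, gender, study day and sitting in the preceding half hour. Both are restricted to seated participants by the exclusion that begins "Decision points where the participant was standing or moving at the time of prompt delivery (sent". The SAP defines neither *response* nor *prompt type*.

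**The concern.** A screening experiment exists to compare its factors. Here the declared primary outcome is modeled only by whether a prompt was sent, and the prompt's characteristics are related only to a different outcome. An analyst who followed the SAP exactly could say whether prompting gets people up. The same analyst could not say, on the primary outcome, whether target, social framing or content makes a difference.

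Three open definitions add to this:

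- **Coding.** *Prompt type* could be three main effects, a factorial with interactions, or eight unordered categories. These answer different questions with very different precision.
- **Response.** The first factor is "behavioral target (sit-to-stand vs. sit-to-light physical activities (LPA", so one level asks for light activity. If only a transition to standing counts, a participant who goes straight from sitting to stepping may be scored as a non-responder, and that would bear unequally on the two levels of this factor.
- **Assignment.** Without a stated mechanism, one cannot tell whether the factors are crossed or at what unit each is randomized.

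If these are left open, the choices could be made after the data are seen.

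**Working it through.** **Step 1. Match aim to model.**

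| Aim 2 element | Model of the binary response | Model of sedentary time |
|---|---|---|
| Sent vs not sent | yes | not stated |
| Behavioral target | no | only if it is part of *prompt type* |
| Social effects | no | only if it is part of *prompt type* |
| Content | no | only if it is part of *prompt type* |

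Factor effects planned on the primary outcome: 0 of 3. This treats *response* as the sit-to-stand outcome. That is an inference, supported by the shared 5-minute window and the seated-only restriction. If *response* means something else, the primary outcome has no model at all.

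**Step 2. Reproduce the plan's only Part B count.** 8 hourly points × 5 days × 4 weeks = 160 decision points per participant. At a sending probability of 0.5, 160 × 0.5 = 80, the number in Protocol section 7. Both the 0.5 and the per-participant reading are inferred. Read instead as a total for all 20 participants, 80 would be 80/20 = 4 prompts each, or 4/160 = 2.5% of decision points, which does not fit hourly randomization well. On the per-participant reading, 20 × 80 = 1,600 prompts are sent. No power calculation is given to reproduce.

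**Step 3. Can sedentary time stand in for the primary outcome?** Start seated and assume that those who rise stay up. Mean 5-minute sedentary time = 5 − (proportion rising) × (5 − mean time of rising). The values are assumed:

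- Level 1: 30% rise at 3.5 min on average: 5 − 0.30 × 1.5 = 4.55 min.
- Level 2: 20% rise at 2.75 min on average: 5 − 0.20 × 2.25 = 4.55 min.

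The mixed model expects no difference. The primary outcome differs by 0.30 − 0.20 = 10 points, with odds ratio (0.30/0.70)/(0.20/0.80) = 1.71.

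**Step 4. What precision would the missing analysis have?** For balanced levels, 80% power, two-sided 5% and no design effect, the detectable difference is 2.80 × √(4p(1 − p)/N), where p is the response rate and N the number of sent prompts analyzed. Neither document gives p or the share of prompts that arrive while the participant is sitting, so both are assumed.

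| p | N = 1,600 (all) | N = 1,440 (90% sitting) | N = 800 (50% sitting) |
|---|---|---|---|
| 0.10 | – | 4.4 points | 5.9 points |
| 0.25 | 6.1 points | 6.4 points | 8.6 points |
| 0.40 | – | 7.2 points | 9.7 points |

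Bonferroni over three tests replaces 2.80 by 3.236, about 15% more. At p = 0.25 this gives 7.4 points (N = 1,440) to 9.9 points (N = 800).

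**Step 5. Does the coding matter?** Three crossed two-level factors make 2 × 2 × 2 = 8 types. With equal allocation, 1,600 prompts give 800 per factor level but 200 per type. For an assumed 20% vs 25%, with all prompts analyzable and independent, power is 67% for one factor's main effect and 22% for one type against another.

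**The case against.** The strongest reply is that the factor question is not ignored. Aim 2 speaks of an acute reduction in sedentary behavior, and the SAP does relate prompt type to sedentary time over the same 5 minutes. The protocol names its primary outcome in a separate sentence and does not say that each factor must be tested on it. This stands in part: the plan does give some evidence on prompt type. But that evidence is not on the declared primary outcome, and with the coding unstated it may not separate the factors.

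The example in Step 3 was chosen to cancel exactly. With equal rising times of 2.75 minutes, the same 10-point gap would appear as 0.10 × 2.25 = 0.225 minutes of sedentary time. So the example shows that the two outcomes can disagree, not that they are likely to.

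The precision figures rest on the inferred 1,600, balanced levels and independent observations. Within-person correlation would change them, and they would not apply to group vs individual if that factor is assigned to people or clusters. This is right, but the missing term does not depend on those figures.

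A model restricted to sent prompts compares levels with one another, not with no prompt. That is why the sent vs not-sent GEE should stay. One model with not-sent points as the reference and factor contrasts among sent prompts would also serve.

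Finally, the protocol calls the studies exploratory, and appendices not supplied may describe factor assignment. The first point makes formal multiplicity control, and models for stand time and steps, matters of lesser weight. The second limits the claim on assignment to the text available. Neither explains why the factors are absent from the primary-outcome model.

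**Conclusion.** The concern holds. As written, the SAP estimates the overall effect of sending a prompt on the binary response, and an association of an uncoded prompt type with sedentary time. It estimates none of the three factor effects on the primary outcome. The sent vs not-sent result is not undermined, and no figure in the plan is wrong; this is a gap in specification that should be fixed before the data are analyzed.

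The count of 0 of 3 rests on the text, plus the reading of *response* as the primary outcome; any other reading makes the gap larger. The 10-point disagreement and the detectable differences of 4.4 to 9.7 points are illustrations under stated assumptions, not predictions.

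**What to change.** 1. **Settle assignment first.** Reconcile Protocol section 7, Part B, with Aim 2: state how factor levels are assigned, whether they are crossed, and the unit of allocation for each, including group vs individual.
2. **Define *response*** to match the Aim 2 primary outcome, and state how a direct move from sitting to stepping is counted.
3. **Add the missing model.** Keep the sent vs not-sent GEE. Add a 5-minute GEE among prompts sent to seated participants, with main effects for target, social and content, and name it as the Aim 2 primary-outcome analysis. Treat two-way interactions as secondary, and fit them only if the factors were crossed.
4. **Code *prompt type*** in the mixed model by the same three factors or equivalent contrasts, with the reference level given and the handling of not-sent decision points stated.
5. **State how multiplicity** across the three factor tests is handled, even if the answer is that the results are exploratory and unadjusted.
6. **Secondary:** model stand time and steps by the same factors.

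The cost is SAP wording and a few extra model runs, with no new participants or assessments. It depends on a record of the factor levels carried by each sent prompt, which neither document describes. The downsides are a few more estimates to report and, if Bonferroni is used, a detectable difference about 15% larger.
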